#### Table 1. Treatment Regimens for IV Test Article

BID = twice a day dosing, NS = Normal saline (0.9% sodium chloride) for injection, t = time.

a See Section 7.6.2 for allowed adjustments in iv dosing schedules.

b All 100 mg in 100 mL infusions of omadacycline or 100 mL NS placebo are administered continuously over 30 minutes (± 5 minutes). On Day 1, if QD dosing is selected, the 200 mg in 100 mL infusion of omadacycline or matched placebo will be administered continuously, without interruptions, over 60 minutes (± 5 minutes).

All 250 mL infusions of moxifloxacin or 250 mL NS placebo are administered continuously over 60 minutes (± 5 minutes).

### 7.6.2 Selection and Timing of iv Dose for Each Subject

To facilitate study enrollment at all times of the day and permit subjects to be "shifted" to a more practical dosing schedule consistent with hospital schedules, a provision is made for limited

adjustment of the dosing interval. Specifically, infusion times may be adjusted up to  $\pm 2$  hours per infusion interval until the desired administration schedule is achieved.

Once the desired start of infusion time is determined, subsequent infusions should be "anchored" to that time. That is, thereafter, the start of infusion should be within  $\pm 1$  hour of the specified target infusion time.

### 7.6.3 Management While on iv Test Article

While the subject is receiving iv therapy, the investigator will assess the subject daily and choose one of the following outcomes based on the overall clinical response of the subject:

- Continue iv test article
- Assess for po test article using the protocol defined criteria (after a minimum of 2 days of iv therapy), see Section 7.6.5.
- Discontinue test article this decision will prompt the EOT evaluation (even if the subject does not complete the minimum of 7 days of dosing)

At all times during the study the decision to continue iv, switch to po, or discontinue test article is made based on the patient's response including the attainment of clinical stability and the clinical judgment of the investigator. Each daily decision is to be recorded on source documents and the information to be transferred to eCRFs by blinded study site personnel.

#### 7.6.4 Investigator's Decision to Continue or Discontinue Treatment

At all times during the study the decision to continue iv, switch to po, or discontinue test article is made based on the patient response including the attainment of clinical stability and the clinical judgment of the investigator.

The investigator may use microbiological results (e.g., culture and susceptibility results) from the local microbiology laboratory to help guide therapy; however, investigator decisions to continue or discontinue test article should be based on *clinical response* rather than susceptibility results. For example, if a respiratory pathogen is detected after randomization that is not susceptible to omadacycline and/or moxifloxacin and the subject is stable or clinically improving, blinded study treatment may continue unless the investigator perceives an undue risk to the subject.

Similarly, if a viral respiratory pathogen is detected after randomization (including but not limited to SARS-CoV-2), study drug may be continued if the investigator continues to suspect co-infecting bacterial pathogen(s) and the subject is stable or clinically improving, and concomitant treatment for the viral pathogen may be administered as appropriate. Questions about individual cases should be discussed with the Medical Monitor prior to discontinuing study drug or administering additional antimicrobial agents, and decisions should be recorded in source documents.

### 7.6.5 Investigator's Decision to Switch from iv to po Treatment

Initially, all randomized subjects will receive at least 2 days of iv antibacterial therapy. Beginning on the Day 3 visit, the subject may be eligible to switch from iv to po therapy. The decision to switch to po treatment will be made by the investigator; the subject should be considered clinically stable and meet all criteria for transition to a po regimen. Specifically, the subject must meet the following requirements, and this should be noted in source documents and recorded on the eCRF:

- Temperature  $\leq 37.8^{\circ}C (100^{\circ}F)$
- Heart rate  $\leq 100$  beats/minute
- $RR \le 24$  breaths/minute
- SBP  $\geq$  90 mm Hg
- Oxygen saturation  $\ge 90\%$  as measured by pulse oximetry or PaO2  $\ge 60$  mm Hg by ABG
- Normal ("absence of confusion") or return to baseline mental status
- Ability to maintain po intake.

The first po dose should be administered in the morning, 12 to 24 hours after the last dose of iv test article. Switch to po will not be permitted until after the subject has completed at least the 2 days of iv treatment. The date and time the investigator confirmed the criteria for the subject's eligibility for po treatment were met and made the decision to switch to po treatment will be recorded on source documents and the information transferred to eCRFs by study site personnel.

### 7.6.6 Oral Treatment Phase

Treatment regimens for po dosing are shown in Table 2 below. When switching from iv to po test article, the recommended interval between doses will be maintained. The first po dose, for both omadacycline and moxifloxacin treatment arms, should be given in the morning 12 to 24 hours after the last dose of iv test article.

The po treatment phase will employ a double-blind, double-dummy design. To maintain investigator and subject blinding, subjects in both arms will receive 2 tablets and 1 overencapsulated tablet in the morning, as shown in Table 2 below. All doses of oral test article should be taken with water.

All oral doses should be taken in a fasted state. Fasting is defined as no food, antacids or multivitamins containing multivalent cations (eg, aluminum, magnesium, calcium, bismuth, iron, or zinc) or drink except water for at least 4 hours before dosing. After dosing, no food is permitted for 2 hours as well as no dairy products, antacids or multivitamins containing multivalent cations (eg, aluminum, magnesium, calcium, bismuth, iron, or zinc) for 4 hours.

Time of Dosing	Omadacycline Arm	Moxifloxacin Arm	Dosing Condition a,b
Morning (upon awakening) a	Two 150 mg omadacycline tablets and 1 over-encapsulated placebo tablet	One 400 mg over-encapsulated moxifloxacin tablet and 2 placebo tablets	Fasting overnight (no food or drink except water) before dosing; after dosing, no food for 2 hours, no dairy products for 4 hours

 Table 2.
 Treatment Regimens for Oral Test Article

po = per oral.

a All doses of po test article should be taken with water.

b All subjects will be instructed to avoid taking antacids and multivitamins while taking po test article.

#### 7.6.6.1 Management While on Oral Test Article

When subjects are switched to po therapy, subjects will be given instructions on how to administer the po therapy, a subject diary to record dates and times of po treatment, and a day supply of po test article. Study personnel will review the dosing diary and tablet count with the subject when the po therapy is first dispensed to the subject and at subsequent visits until the subject has completed therapy. Study personnel will review and record which medication is taken in the eCRF.

While the subject is receiving po therapy, the investigator will assess the subject and choose one of the following outcomes based on the overall clinical response of the subject:

- Continue po test article
- Discontinue test article this decision will prompt the EOT evaluation (even if the subject does not complete the minimum days of dosing)

At all times during the study the decision to continue or discontinue test article is made based on the clinical judgment of the investigator. Each daily decision is to be recorded on source documents and the information transferred to eCRFs by blinded study site personnel.

## 7.7 Dose Adjustments and Interruptions of Test Article

No dose adjustments or planned interruptions of test article will be permitted during this study.

## 7.8 Method of Assigning Patients to Treatment Groups

All eligible subjects will be randomized via an IxRS that assigns them to 1 of the treatment arms (in a 1:1 ratio). The site delegate will contact the IxRS after confirming that the subject fulfills all the inclusion criteria and has none of the exclusion criteria. The IxRS will assign a test article to the subject based on a computer -generated randomization schedule. The randomization will be a blocked randomization sequence stratified by PORT Risk Class (III or IV) and receipt of an allowed antibacterial (see Appendix 4) in the 72 hours prior to study treatment as defined in the

IxRS specifications and Statistical Analysis Plan (SAP). Subjects randomized into the study will be assigned the treatment corresponding to the next available number from the computergenerated randomization schedule. The subject is considered randomized when the IxRS provides the test article assignment, regardless of whether the subject actually receives any medication. Randomization of subjects who have received an allowed antibacterial therapy in the 72 hours prior to study treatment will be capped at 25% of the subjects randomized.

### 7.8.1 Subject Numbering

Upon signing the informed consent, the subject will be assigned a unique subject number. Subjects who have been pre-screened, but who do not sign an ICF will not be assigned a subject number. A subject who discontinues participation or is withdrawn before receiving a treatment assignment, and who is re-screened at a later time will be assigned a new subject number and recorded as re-screened. Re-screening is at the discretion of the investigator and in consultation with the medical monitor. The investigator will maintain a subject master list to document every subject who has signed an ICF. A copy of this list should be retained in the investigator's study files.

## 7.9 Dispensing Test Article

Each study site will be supplied by the sponsor with the investigational product and comparator. The IxRS will instruct the pharmacist or designee as to the appropriate therapy, omadacycline or comparator, to be administered. The unblinded site pharmacist or designee will prepare the test article as instructed. The unblinded pharmacist or designee will provide the blinded nurse administering the infusion with the appropriate solutions for each subject covered to conceal the identity of the test article using materials provided by the sponsor and labeled with blinded administration instructions. The po test article will be supplied to the sites in kits that contain bottles of active omadacycline tablets or matched placebo tablets, and bottles of active overencapsulated moxifloxacin tablets or matched over-encapsulated placebo tablets. Oral test article supplies are completely blinded. Therefore, oral test article supplies can be transferred from the unblinded study personnel to blinded study personnel for storage, dispensation, and reconciliation. The study coordinator/staff will instruct the subject on the use of po test article. The procedures are detailed in the Pharmacy Manual.

## 7.10 Blinding

The investigator and sponsor will be blinded to treatment arm assignments in both the iv and po phases of the study.

The sponsor designee (eg, study statistical team, IxRS vendor, etc) will have a designated randomization administrator who will maintain the randomization codes in accordance with standard operating procedures to ensure the blind is properly maintained, and that only sponsor personnel who require knowledge of treatment assignments will be unblinded (eg, staff involved in maintaining the randomization codes).

Because the color of the iv test article infusions and placebo infusions differ, all infusion bags and iv tubing will be covered with materials provided by the sponsor so that subjects and blinded
study personnel will not know the identity of the test article being administered. The infusion regimen will follow a blinded design with subjects in each study arm receiving the same infusion volumes with the same administration instructions. Blinded study personnel will administer the infusions and collect, review and enter data regarding the iv infusions (eg, start and stop times) into an eCRF. If gravity administration is not the standard of care, then an infusion pump may be used. If an infusion pump is used, then an unblinded administrator will be required. Personnel identified as unblinded administrators will not participate in any study procedures other than iv administration of test article and the collection, review and entry of iv related data (eg, start and stop times) into an eCRF.

During the po phase, a double-blind, double-dummy design will be used to ensure the blind is maintained. Subjects in the omadacycline arm will receive active omadacycline tablets and matched comparator over-encapsulated placebo tablets. Subjects on the moxifloxacin arm will receive omadacycline placebo tablets and active over-encapsulated moxifloxacin tablets.

The unblinded source documentation binder containing all descriptions of pharmacy preparations and infusions or distributions of test article and any unblinded subject randomization data should be stored separately, and under lock and key, separate from the documents containing blinded information.

Data that could potentially lead to unblinding will not be accessible to anyone other than the following site personnel:

- unblinded study pharmacist or designee
- unblinded study monitor
- unblinded administrator(s)

Unblinding by site personnel is only to occur in the case of subject emergencies (see Section 7.11, below) and at the conclusion of the study.

# 7.11 Emergency Unblinding of Treatment Assignment

Emergency unblinding should only be undertaken when it is essential to treat the subject safely and efficaciously. Most often, test article discontinuation and knowledge of the possible treatment assignments are sufficient to treat a study subject who presents with an emergency condition. It is encouraged for the investigator, when contemplating unblinding, to contact the sponsor or sponsor's designated Medical Monitor or designee to confirm the need to unblind, prior to unblinding (see Section 2 for contact information). However, if required, the investigator can unblind without consulting the Medical Monitor.

Emergency code breaks are performed using the IxRS. When the investigator contacts the system to unblind a subject, he/she must provide the requested subject identifying information and confirm the necessity to unblind the subject. The investigator will then receive details of the drug treatment for the specified subject and a fax or e-mail confirming that the treatment assignment of the subject was unblinded. The system will automatically inform the sponsor's monitor for the site and the sponsor that the code has been broken.

It is the investigator's responsibility to ensure that there is a procedure in place at their site to allow access to the IxRS code break information in case of emergency. The investigator will inform the subject how to contact his/her backup in cases of emergency when he/she is unavailable. The investigator will provide protocol number, test article name if available, subject number, and instructions for contacting the sponsor (or any entity to which it has delegated responsibility for emergency code breaks) to the subject in case emergency unblinding is required at a time when the investigator and backup are unavailable.

All steps outlined above will be followed, including contacting the Medical Monitor as soon as possible and not more than 24 hours afterwards. It will be the responsibility of all study personnel to ensure that, except for the above procedure, investigator blinding is maintained until after study completion.

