#### 8.21.5 Worsening or Progression of Disease Under Study

Worsening or progression of the qualifying CABP should be recorded as a clinical failure (as part of the efficacy assessment), rather than an AE, unless the worsening/progression also meets the criteria for a serious AE (in which case the event also should be reported as an SAE). In contrast, any new or secondary infections that the investigator considers to be distinct from the qualifying CABP should be reported as AEs in all cases, whether non-serious or serious.

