6.1.4.3 Concomitant Antibiotic Therapy

Subjects who receive any systemic concomitant antibiotic therapy from the time of the first dose of test article through the time of the last dose of test article at EOT and through the PTE Visit with a spectrum of activity against the known or potential infecting pathogen(s) responsible for the CABP under study will be excluded from the CE-EOT and CE-PTE populations, respectively, unless the subject receives the antibiotic therapy for treatment of the CABP due to insufficient therapeutic effect of the test article (ie, for progression or development of new symptoms of CABP or development of infectious complications of CABP).

Subjects who receive a systemic concomitant antibiotic that is not effective against the baseline pathogen, or if no pathogen is isolated, and the antibiotic does not have activity against CABP pathogens, will be included in the CE-EOT and CE-PTE populations.

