6.1.4.4 Test Article Therapy

Subjects must meet all of the following to be included in the CE populations:

- Received at least 1 dose of active test article and the correct test article based on the randomization assignment.
- Study personnel involved in the assessment of efficacy remained blinded to study treatment, unless a treatment limiting adverse event (AE) occurred which required emergency unblinding.
- Evaluable failure: The subject received the first 2 doses (if receiving 200 mg iv QD on Day 1) or 3 doses (if receiving 100 mg iv on Day 1) of active test article (omadacycline group) or first 2 doses of active test article (moxifloxacin group) and the investigator classifies the subject as a Clinical Failure at the EOT Visit (CE-EOT population) or the overall Clinical Response (based on the investigator's assessment) at the PTE Visit (CE-PTE population) is Clinical Failure.
- Evaluable success: The subject received the first 3 doses (if receiving 200 mg iv QD on Day 1) or 4 doses (if receiving 100 mg iv on Day 1) of active test article (omadacycline group) or the first 3 doses of active test article (moxifloxacin group) and the investigator classifies the subject as a Clinical Success at the EOT Visit (CE-EOT population) or the overall Clinical Response (based on the investigator's assessment) at the PTE Visit (CE-PTE population) is Clinical Success.

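### A treatment failure documented under blind before a code break for efficacy can be dropped from the CE population, because the SAP excuses unblinding only after a treatment-limiting AE

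*Protocol*

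**What the plan says.** **Ground for a code break (protocol 7.11).** "Emergency unblinding should only be undertaken when it is essential to treat the subject safely and efficaciously". No adverse event is required. Contact with the Medical Monitor is encouraged, but "However, if required, the investigator can unblind without consulting the Medical Monitor". After the break, "The investigator will then receive details of the drug treatment for the specified subject". The investigator also rates clinical response at EOT and PTE (protocol 8.13.1.2 and 8.13.1.3).

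**CE entry (SAP 6.1.4.4).** "Subjects must meet all of the following to be included in the CE populations". One listed condition is that staff who assess efficacy "remained blinded to study treatment, unless a treatment limiting adverse event (AE) occurred which required emergency unblinding". There is no exception for lack of efficacy, and no rule about whether the outcome was settled before or after the break.

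**Worsening pneumonia (protocol 8.21.5).** Such an event "should be recorded as a clinical failure (as part of the efficacy assessment), rather than an AE". Only when it is serious is it reported as an SAE as well.

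**Other CE rules keep failures.** SAP 6.1.4.3 excludes subjects given other active antibiotics, "unless the subject receives the antibiotic therapy for treatment of the CABP due to insufficient therapeutic effect of the test article". SAP 6.1.4.4 itself defines an evaluable failure by a minimum number of doses. SAP 6.1.4.5 waives the PTE visit window for EOT failures. The ME populations are subsets of CE (SAP 6.1.5).

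**The concern.** The protocol's ground for breaking the code is wider than the SAP's ground for forgiving it. A subject can fail, have that failure documented while everyone is blinded, and then be unblinded so that rescue can be chosen. In that subject the blind has already protected the rating. Yet the blinding condition overrides both the rescue rule in 6.1.4.3 and the evaluable-failure rule, so the subject leaves CE and ME.

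Where the exclusion works through this route it depends on outcome. The arm with more failures can lose more of them even if unblinding is equally likely in both arms, and that pulls the CE difference towards zero. For the EMA claim, protocol 12.6.3 requires non-inferiority in both ITT and CE, so a CE result biased towards similarity weakens one of the two required tests, provided the EMA analysis uses this CE definition.

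**Working it through.** **Step 1: the texts side by side**

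| Situation at the code break | Covered by protocol 7.11? | Excused by SAP 6.1.4.4? | CE status |
|---|---|---|---|
| Treatment-limiting AE required it | Yes | Yes | Kept, if other CE rules are met |
| Non-serious CABP worsening, failure already documented | Yes, if essential to treat efficaciously | No, since 8.21.5 does not make it an AE | Dropped |
| CABP worsening that is also an SAE | Yes | Only if read as a treatment-limiting AE | Unclear |

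The second row is the gap. The third is an ambiguity that the SAP does not settle.

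**Step 2: reproduce the plan's CE power**

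Inputs from SAP 5.1.1: 89% success in both arms, 536 evaluable subjects (268 per arm at 1:1), margin 10 points, one-sided alpha 0.025. The text of protocol 12.2 gives 80% for CE, but its Table 4 and the SAP give 89%. The stated power reproduces only with 89%; 80% gives 82.0%.

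Farrington-Manning power = Φ[(p1 − p2 + 0.10 − 1.96·s0)/s1]. Here s0 is the standard error under the constrained null estimates and s1 the one under the assumed rates.

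With 0.89 in both arms, the constrained rates are 0.8228 and 0.9228, s0 = 0.02846 and s1 = 0.02703. Then (0.10 − 0.0558)/0.02703 = 1.636, so power is 94.9%, as stated.

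**Step 3: size of the effect on the CE test (assumed shares)**

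The documents give no unblinding rate, so the share g of failures dropped is an assumption. If an arm has success rate p and loses share g of its failures:

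- rate becomes p/[1 − (1 − p)g]
- n becomes 268·[1 − (1 − p)g]

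Take true CE rates exactly at the margin, 79% omadacycline and 89% moxifloxacin, with the same g in both arms:

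| g | Failures dropped (omadacycline / moxifloxacin) | Rates after dropping | Difference, points | One-sided error, CE test alone |
|---|---|---|---|---|
| 0 | 0 / 0 | 79.0% / 89.0% | -10.0 | 2.5% |
| 3% | 1.7 / 0.9 | 79.5% / 89.3% | -9.8 | 2.9% |
| 5% | 2.8 / 1.5 | 79.8% / 89.5% | -9.7 | 3.2% |
| 10% | 5.6 / 2.9 | 80.7% / 90.0% | -9.3 | 4.2% |

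Check at 5%: s0 = 0.03100 and s1 = 0.03098, so (−0.09654 + 0.10 − 1.96·0.03100)/0.03098 = −1.85, which is 3.2%.

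**Step 4: a single subject near the boundary**

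With 227/268 against 239/268 the difference is -4.5 points and the Miettinen-Nurminen lower limit is -10.3%, so non-inferiority is not shown. Dropping one omadacycline failure (227/267) gives a lower limit of -9.95%, and it is shown.

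Steps 3 and 4 are unstratified. The EMA analysis in protocol 12.6.3 is stratified, so the figures are approximate for it.

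**The case against.** **The affected group may be nearly empty.** Protocol 7.10 limits site unblinding to emergencies (and study end). Protocol 7.11 says that stopping test article and knowing the possible assignments is usually enough. Protocol 7.14 already covers a non-responder without a code break: the subject is a Clinical Failure, test article stops, and further treatment is at the treating physician's discretion. Worsening grave enough to need a break will often be an SAE under 8.17 and might then be read as a treatment-limiting AE. This stands as a reason to expect few cases. It does not close the gap for non-serious worsening, and the SAP does not adopt the helpful reading for serious worsening.

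**A reader might infer that the rule removes only failures.** It does not. The condition takes no account of outcome. For example, protocol 8.19 lets the investigator obtain the assignment after an overdose, and a success unblinded that way is also excluded.

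**A reader might infer that the failure is always settled before the break.** The documents do not say so. Response is selected at the EOT or PTE visit, and needing alternative treatment is a judgement that could be made or recorded with the arm known. Excluding those subjects is defensible. The point covers only failures documented beforehand.

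**A reader might infer that AE-unblinded subjects simply stay in CE.** Under SAP 6.1.4.3, those switched to an active antibiotic because of the AE are excluded anyway.

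**Exclusions would be visible.** SAP 8.1 tabulates and lists reasons for exclusion, and SAP 6.2 provides blinded evaluability review. That helps detection but does not change who is analysed.

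**Conclusion.** The mismatch is real: as written, a failure documented under blind before an efficacy-driven code break can be dropped from CE and ME, contrary to the intent of 6.1.4.3 and the evaluable-failure rule. Serious progression is kept only if someone reads it as a treatment-limiting AE. A separate assessor who remained blinded would avoid the exclusion.

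The expected effect is small. ITT, including the FDA primary ECR analysis, is unaffected. CE intervals in this SAP are descriptive (SAP 9.3). The EMA analyses sit in a separate SAP (SAP 3) that was not available, so whether it repeats the rule is unknown.

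It is tempting to read 2.9% to 4.2% as the error rate of the EMA decision. The documents do not support that. The figures apply to the CE test alone, on assumed shares of 3% to 10%. The EMA claim also needs ITT, where these subjects still count as failures. If the ITT difference is at the margin too, a false claim cannot be more likely than the ITT test's nominal 2.5%.

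**What to change.** Extend the exception in SAP 6.1.4.4 to subjects for whom the investigator had recorded, with a date and time before the IxRS code break, that a Clinical Failure criterion was met. One example is a recorded decision that alternative antibacterial therapy for CABP was required for insufficient effect. Keep these subjects in CE as failures if they meet the evaluable-failure dose rule. Timing should rest on that recorded decision, not on the start of rescue, which may follow the break.

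Also:

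- State whether CABP progression reported as an SAE counts as a treatment-limiting AE for this rule.
- Put the same clause in the EMA SAP.
- Report CE exclusions for unblinding by arm and outcome.

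The change must be made before database lock and unblinding, when evaluability is fixed (SAP 6.2.2). The cost is one SAP clause plus work to establish the order of events. Code breaks go through the IxRS, and daily treatment decisions go to source and eCRF (protocol 7.6.3 and 7.6.6.1). Those sections do not expressly require a clock time or the failure criterion, so source review may be needed for the few subjects concerned. CE success rates may be slightly lower.
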